## **STUDY PROTOCOL**

### **1. Brief Summary of the Proposed Research**

This is a pilot randomized controlled trial of an intervention to improve arm function in children ages 6 to 17 with cerebral palsy and upper limb hemiparesis. Twenty participants will be randomized to either a group treated with neuromuscular electrical stimulation and video games or video games alone. Both groups will receive 6 wks of treatment. Changes in upper extremity motor impairment and function will be assessed for each participant at baseline, mid treatment, end of treatment and at 3 mo follow-up.

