### **Rationale**

Cerebral palsy is the leading cause of disability in children, one third of whom suffer from hemiparesis. Video games and functional electrical stimulation are complimentary approaches that have independently improved outcomes in hemiplegic cerebral palsy children [1], [2]. We propose a unique intervention that combines custom hand therapy video games with contralaterally controlled functional electrical stimulation (CCFES). CCFES assists hemiparetic children to open their paretic hand in direct proportion to the degree of voluntary unimpaired hand opening, as detected by a sensor glove worn on the child's unimpaired hand. This is designed to facilitate motor control learning by linking movement intent to motor execution and returning somatosensory and proprioceptive sensations back to the brain.

In order to facilitate exercise with CCFES at home, we developed finger-motion controlled video games that are played with the assistance of CCFES. The video games are played by opening and closing the paretic hand, and facilitate motor practice based on learning principles (goal-oriented movement, intense repetition, task variation, engagement and motivation, and appropriate task difficulty). The finger motions are captured by a sensor that is attached to a fingerless glove worn on the paretic hand.

Because hand therapy video games without CCFES assistance may also be an efficacious therapy in this population, we propose a randomized clinical study comparing CCFES + video games to video games without CCFES.

This will be the first controlled trial of the CCFES + Video Game treatment in cerebral palsy. The purpose of the study is to estimate its efficacy in improving arm/hand movement and function.

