### Specific Aims

The primary aim of this study is to collect pilot data to estimate the efficacy of CCFES videogame therapy in improving outcomes of upper extremity impairment and function. CCFES + videogame therapy is new, so estimating its effect is a first step to test our hypothesis that it leads to greater outcomes than video game therapy alone. We will assess clinical measures of upper extremity impairment, function, and community use to test this hypothesis.

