### Methods and Procedures

Both the experiment group and control group interventions last 6 weeks and consists of therapist-guided sessions in the rehabilitation clinic and self-administered or caregiver-assisted sessions at home. While both groups will receive the same task practice and video game training, only the experiment group will receive an electrical stimulation device to assist with hand opening during practice. An adaptive randomization algorithm will be used to balance the two groups with respect to age, gender, and baseline severity (not severe if the child is Manual Activity Classification System level I-II, severe if level III-V). The treatment dose will be the same for both groups: 10 sessions per wk of self-administered video game training at home plus 2 lab sessions per wk for the first 3 wks and 1 lab session per wk for the final 3 wks – 58 hrs total. Blinded assessment of upper limb impairment and function will be done at baseline, mid-treatment, end-of-treatment, and 3-mos post-treatment.

- Note: Contralaterally controlled electrical stimulation (CCFES) – Enables patients with upper extremity hemiplegia to open their paretic hand by stimulating finger and thumb extensors with surface electrodes. Stimulation is proportional to degree of unimpaired hand opening as detected by an instrumented glove worn on the unaffected hand. Thus, volitional opening of the non-paretic hand produces stimulated opening of the paretic hand. CCFES is used during functional task practice and hand therapy video games to link motor intent with execution.
- Note: Hand Therapy Video Games – Four intuitive and engaging games were developed specifically for play with CCFES to provide goal-oriented motor skill training, impairment-appropriate difficulty, and performance feedback that motivates iterative play and skill improvement. Paddle Ball (i.e., Pong) is a simplified tennis simulation that uses hand movement to control a vertically moving paddle. Skee Ball uses hand-opening speed to launch balls at targets. Sound Tracker requires the

hand to precisely follow a moving track generated by different songs. Marble Maze uses hand opening to rotate mazes and guide marbles out into a bucket.

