Additionally, we will assess the following hand muscle co-activation measures during lab visits prior to treatment:

Intervention outcomes that are assessed at baselines, end of treatment, and follow up will include the following.

- Melbourne Assessment 2: This is an assessment of unilateral upper extremity function for children ages 2.5 to 15. Participants will perform 14 tasks using their weaker arm and hand, each of which is scored on a 3,4 or 5 point scale. The tasks involve using the hand to reach different positions (reaching, pronation, supination) and manipulate pellets and crayons. This assessment takes 15 minutes to perform.[9]
- Finger movement tracking accuracy: Finger movement tracking is a method of measuring motor control. Using the same bend sensor used for controlling the video games, the relative degree of finger extension will be displayed as a cursor on a computer screen, its vertical position corresponding to the degree of finger extension. A sinusoidal trace having a frequency of 0.1 Hz (1 cycle in 10 seconds) will scroll across the screen. The amplitude of the sine-wave track will be scaled so that it oscillates between 15% and 85% of the participant's full active finger extension. The participant will be seated with the wrist and forearm stabilized in a neutral posture. The participant's task is to keep the cursor on or as close to the scrolling trace as possible by extending and flexing their index finger. The vertical distance between the cursor and the target trace will be calculated for every time point of data collected. The final error for each 30-sec trial will be the average vertical distance (percentage of the participant's range of motion) from the cursor to the target trace. Three trials will be administered after a practice trial, resting 1 minute between trials. This test takes approximately 5 minutes.
- Box and Block Test: The Box and Block test is a measure of gross manual dexterity, which requires the participant to pick up 1 block at a time, move it over a partition, and release it in a target area as many times as possible in a 1-minute period. The Box and Block test measures changes in functional grasp and release but not during activities of daily living (ADL), and therefore cannot be strictly categorized as either an impairment or activity limitation measure. This test takes approximately 5 minutes.

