## **STATISTICAL ANALYSIS**

### **Sample size determination**

This is a pilot randomized control trial that aims to estimate the intervention effect necessary to power a larger trial. The sample size target of 20 participants was limited by the amount of funds provided by the R21 funding mechanism.

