### **Data analysis**

We will use a descriptive approach using means and standard errors to assess the effect of hand opening repetitions on the treatment group over time for each outcome. Due to the small sample size in our dataset, we will use a robust estimator to calculate the standard errors.

Upper extremity motor function will be assessed at enrollment, 6 weeks (end of treatment), and at 12 weeks post-treatment by a blinded assessor therapist. All assessments will be performed without any assistance from the stimulator and assessments will take place at least 24 hours after their last treatment session in order to avoid any transient carry-over effect or muscle fatigue. Change scores from the following outcomes will be calculated for each subject.

Descriptive statistics will be used to describe the results across patients and paired t-tests will be used to analyze the pre-post changes.

- Finger movement tracking error (squared sum distance from the target).
- Box and Block Test number of blocks successfully moved.
- Melbourne Assessment 2 percent score (0-100%).
- Assisting Hand Assessment score.

Additionally, adherence will be determined by downloading usage data from both the stimulator and the computer (via a portable USB thumb drive) – which will be used to calculate the percentage of prescribed treatment time completed by each participant. Participants will also be asked at every visit to report any difficulties or complications they may have experienced during home treatment sessions. Then, at the end of treatment, every participant will be interviewed regarding their impression of treatment and dosage, how easy or difficulty it was to use the equipment and play the games, and what changes they would suggest to the equipment or treatment dose, and whether or not they thought the treatment made any difference in their hand function. The number of hand opening repetitions will be recorded at each training session.

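### The plan has no between-arm analysis: its only inferential test is a paired pre-post t-test, so the effect of adding CCFES to video games has no prespecified estimate

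*Combined protocol and SAP*

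**What the plan says.** The purpose is comparative throughout.

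- Brief Summary: "Twenty participants will be randomized to either a group treated with neuromuscular electrical stimulation and video games or video games alone".
- Rationale: "we propose a randomized clinical study comparing CCFES + video games to video games without CCFES". The reason given for the control arm is that "hand therapy video games without CCFES assistance may also be an efficacious therapy in this population".
- Specific Aims: the hypothesis about CCFES with games is that "it leads to greater outcomes than video game therapy alone", and the clinical measures are to be assessed to test it.
- Methods and Procedures: "An adaptive randomization algorithm will be used to balance the two groups with respect to age, gender, and baseline severity".
- Sample size determination: the pilot "aims to estimate the intervention effect necessary to power a larger trial". The target of 20 was set by available funding.

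The Data analysis section then lists:

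- means and robust standard errors, to describe how hand-opening repetitions affect the treatment group over time;
- a change score per child for four outcomes (finger tracking error, Box and Block Test, Melbourne Assessment 2, Assisting Hand Assessment);
- one inferential method: "Descriptive statistics will be used to describe the results across patients and paired t-tests will be used to analyze the pre-post changes".

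Outcome Measures adds that repetition counts will be used in correlations.

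**The concern.** The test that is named does not address the question that is asked. A paired t-test compares each child with his or her own baseline. The change it detects mixes any CCFES effect with the effect of the games, task practice, familiarity with the tests, and time. The control arm exists to remove those shared components, but the plan never subtracts it.

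The plan also does not say whether the paired tests are pooled over both arms or run within each arm. A pooled test can be significant when CCFES does nothing. Separate tests can give a significant result in one arm and not in the other by chance, which invites a false reading of a treatment difference.

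Two things are at stake. The hypothesis in Specific Aims would go untested, and the intervention effect that the pilot is meant to supply for a larger trial would have no prespecified estimator. If the contrast is built later, its form, time point and adjustment would be chosen with the data in view, for four outcomes at two post-baseline times.

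**Working it through.** **1. Is there a between-arm analysis anywhere?** The stated aims and the stated methods, side by side:

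| Section | What it asks for or provides |
|---|---|
| Rationale | a comparison of CCFES + games with games alone |
| Specific Aims | a test of superiority over games alone |
| Sample size determination | an estimate of the intervention effect |
| Data analysis | paired pre-post tests; summaries over patients; means and robust standard errors relating repetitions to the treatment group |
| Outcome Measures | correlations with repetition counts |

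No section contains a two-sample test, a baseline-adjusted comparison, a mixed model, a group-by-time term, or an interval for the arm difference. The two statistical sections read as complete, so redaction does not explain the gap.

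**2. Is there a figure to reproduce?** No. The sample size is a funding limit, and no alpha, power, effect size, SD, allocation ratio or dropout rate is given. The rest is therefore illustration. It assumes a two-sided 5% level, 10 per arm, independent arms, and the same true improvement in both arms, so the true CCFES effect is zero. The gain *d* is the mean change divided by the SD of change.

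**3. How often would paired tests be significant with no CCFES effect?** The probability for *n* children is the noncentral-t power with *n* − 1 df and noncentrality *d*√*n*. If that probability is *p* in one arm of 10, the chance that the CCFES arm is significant and the control arm is not is *p*(1 − *p*).

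| *d* | *p*, one arm (n = 10) | CCFES arm only, *p*(1 − *p*) | Pooled (n = 20) |
|---|---|---|---|
| 0.5 | 0.293 | 0.293 × 0.707 = 0.207 | 0.565 |
| 0.7 | 0.506 | 0.506 × 0.494 = 0.250 | 0.844 |
| 1.0 | 0.803 | 0.803 × 0.197 = 0.158 | 0.989 |

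At *d* = 0.2 and 1.5 the CCFES-only figures are 0.080 and 0.013, so the range over 0.2 to 1.5 is about 1% to 25%. A simulation of 200,000 trials per setting gave 0.207, 0.249 and 0.159 for *d* = 0.5, 0.7 and 1.0. In the same simulation, a two-sample test of change favoured CCFES in 0.025 of trials at each setting.

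**4. Sensitivity to dropout.** With 8 completers per arm (assumed), the CCFES-only figures at *d* = 0.5, 0.7 and 1.0 are 0.178, 0.240 and 0.217. The pooled figures (n = 16) are 0.465, 0.745 and 0.962.

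**5. What would a direct estimate look like?** The unadjusted 95% half-width, in SDs of change, is t(0.975, n₁ + n₂ − 2) × √(1/n₁ + 1/n₂):

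- 10 and 10: 2.101 × 0.447 = 0.94
- 8 and 12: 2.101 × 0.456 = 0.96
- 8 and 8: 2.145 × 0.500 = 1.07

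Adjusting for baseline and severity at 10 and 10 leaves 20 − 4 = 16 df. With balanced covariates the half-width is 2.120 × √0.2 = 0.95 residual SD. The power of an unadjusted two-sample test at 10 per arm (noncentral t) is 18.5% for a difference of 0.5 SD of change, 39.5% for 0.8 SD and 56.2% for 1.0 SD. About 1.33 SD is needed for 80%.

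**The case against.** The strongest reply is that this is a pilot. Its size was set by funding, its analysis is announced as descriptive, and it promises no powered comparison, so the absence of a between-arm hypothesis test is not in itself a fault. Per-child change scores are prespecified for four named outcomes, and in a two-arm trial the difference in mean change follows by subtraction. The error rates above also describe a misreading that the plan never says it will make.

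Much of this is fair. A powered test is not required, the ingredients of an estimate are present, and the percentages are rates of a possible misinterpretation under assumed conditions, not error rates of a declared decision rule. A direct comparison with about 10 per arm will also be imprecise.

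The omission still stands. Pilot status does not excuse leaving out the quantity that the pilot says it exists to estimate, and Specific Aims speaks of testing the comparative hypothesis. The ingredients do not fix the contrast, time point, adjustment or interval. The descriptive sentence concerns repetitions and a single treatment group, so it cannot be read as specifying an arm comparison.

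**Conclusion.** The concern holds, and the plan should be corrected before the data are analysed. This conclusion comes from the text alone: every statement of purpose is between-arm, and the only named test is within-child. It does not depend on the numerical illustration.

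The illustration shows that the gap is not a formality. With equal gains in both arms, a significant pooled result is more likely than not at a standardised gain of 0.5 and nearly certain at 1.0. A pattern in which only the CCFES arm is significant can arise up to about ten times as often as the 2.5% for a direct test. That ratio depends on the size of the shared gain: at 1.5 the pattern falls to about 1%. All these figures rest on assumed 1:1 allocation, equal gains and a two-sided 5% level. Losing two children per arm does not change the conclusion.

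**What to change.** In the Data analysis section, for each of the four listed outcomes:

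1. Define the efficacy estimate as the CCFES-minus-control difference at end of treatment, and again at the 3-month follow-up, adjusted for the baseline value of that outcome.
2. State in advance which randomisation factors enter the model. Baseline plus the two-level severity factor leaves 16 df with 20 children; adding age and gender as single terms would leave 14. If numbers fall short, a baseline-adjusted or unadjusted difference in change still closes the gap, provided that the fallback is written down.
3. Report the difference with its 95% confidence interval and the SD, as the input for the larger trial. Say that it is an estimate and not a powered test.
4. Keep the paired changes as description, state that they are by arm, and say that significance in one arm but not the other will not be taken as evidence of a CCFES effect.

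Use mid-treatment values only if these outcomes are collected then. Brief Summary and Methods and Procedures place an assessment at mid-treatment, while Outcome Measures says "Intervention outcomes that are assessed at baselines, end of treatment, and follow up will include the following" and Data analysis lists no mid-treatment visit.

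The cost is SAP wording and a few lines of code. Sample size, visits and procedures stay as they are. The price is two degrees of freedom for baseline and severity (18 to 16) and a visibly wide interval, which reflects what 20 children can show.

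### With no missing-data rule, the planned paired change scores default to returning children, so the 3-month result may rest on a selected subset and may not be comparable with the 6-week result

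*Combined protocol and SAP*

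**What the plan says.** The Brief Summary describes a two-arm randomised pilot: "Twenty participants will be randomized to either a group treated with neuromuscular electrical stimulation and video games or video games alone". The Data analysis section sets the outcome visits: "Upper extremity motor function will be assessed at enrollment, 6 weeks (end of treatment), and at 12 weeks post-treatment by a blinded assessor therapist". It then says "Change scores from the following outcomes will be calculated for each subject", lists four outcomes (finger tracking error, Box and Block, Melbourne Assessment 2, Assisting Hand Assessment), and adds that "paired t-tests will be used to analyze the pre-post changes". It also plans descriptive means and standard errors over time, with this qualification: "Due to the small sample size in our dataset, we will use a robust estimator to calculate the standard errors".

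Under Sample size determination, the aim is given as "This is a pilot randomized control trial that aims to estimate the intervention effect necessary to power a larger trial", and the size is explained by funding: "The sample size target of 20 participants was limited by the amount of funds provided by the R21 funding mechanism".

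The protocol and SAP state no analysis population, expected dropout, missing-data rule or imputation, and no model that uses children with incomplete visits.

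**The concern.** A change from baseline exists only for a child with both values, and a paired t-test uses only such children. With no other rule, a child who misses the 12-week post-treatment visit leaves any 3-month paired analysis. That child's baseline and 6-week scores then contribute nothing to the 3-month estimate, while the same child still counts at 6 weeks. The two time points can therefore rest on different children.

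Some loss is plausible. The Methods and Procedures section asks families for "10 sessions per wk of self-administered video game training at home" plus clinic visits over 6 weeks, and a return about three months later. If the children who stay away responded less at 6 weeks, the 3-month mean among returners is too high. An apparent gain or retention of benefit could then come from a change in who was measured. This matters because the trial's product is an estimate meant to size a larger study.

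**Working it through.** **No figure to reproduce.** The 20 participants are set by funding. The documents give no alpha, power, effect size, SD or dropout allowance.

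**Inputs.** From the documents: 20 children, two arms, visits at enrolment, 6 weeks and 12 weeks post-treatment. Assumed: about 10 per arm, loss of 10–30% at 3 months, correlation ρ of 0.5–0.8 between the 6-week and 3-month changes, and the same true mean change at both visits. Effects are in SD units of change.

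**1. Chance that everyone returns.** With each child at independent risk d, this is (1 − d)^20: 0.95^20 = 36%, 0.90^20 = 12%, 0.80^20 = 1%.

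**2. Numbers left and precision.** The 95% CI half-width for a mean change is t(0.975, n−1)/√n.

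| Loss | Both arms: n | Half-width (SD) | One arm: n | Half-width (SD) |
|---|---|---|---|---|
| 0% | 20 | 0.47 | 10 | 0.72 |
| 10% | 18 | 0.50 | 9 | 0.77 |
| 20% | 16 | 0.53 | 8 | 0.84 |
| 30% | 14 | 0.58 | 7 | 0.93 |

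**3. Bias, extreme case.** Suppose every lost child is among the worst 6-week responders. In a large sample the returners' 3-month mean is too high by ρ·φ(z_p)/(1 − p), where p is the share lost and z_p its normal quantile.

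| Loss | φ(z_p)/(1 − p) | ρ = 0.6 | ρ = 0.8 |
|---|---|---|---|
| 10% | 0.1755/0.9 = 0.195 | 0.12 | 0.16 |
| 20% | 0.2800/0.8 = 0.350 | 0.21 | 0.28 |
| 30% | 0.3477/0.7 = 0.497 | 0.30 | 0.40 |

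With exactly 20 children and ρ = 0.8, simulated order statistics give slightly less: 0.15, 0.27 and 0.38.

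**4. Bias, moderate selection.** Simulation with 20 children, where the children lost are the lowest on 6-week change plus standard logistic noise. The gap is the returners' 3-month mean minus the 6-week mean in all 20. The true gap is zero.

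| Loss | ρ = 0.5 | ρ = 0.7 |
|---|---|---|
| 10% | 0.04 | 0.06 |
| 20% | 0.08 | 0.12 |
| 30% | 0.12 | 0.17 |

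At 20% loss, ρ = 0.7 and a true change of 0.50 SD at both visits, the returners' 3-month mean is 0.61, or 0.73 in the extreme case. A likelihood estimate that also uses the 6-week scores of the lost children returns 0.50 in both. With loss completely at random, the returners' mean is also 0.50.

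**5. Precision when loss is random.** Take 2 of 10 lost in one arm and ρ = 0.8. Returners only: variance 1/8 = 0.125. Likelihood estimate with the regression slope known: (1 − 0.64)/8 + 0.64/10 = 0.045 + 0.064 = 0.109, which is 13% lower. Estimating the slope from the 8 returners adds 0.36 × 0.025 × 1/5 = 0.0018, where 0.025 = (2/10)² × (1/2 + 1/8) is the variance of the shift in means and 1/5 is the expected inverse sum of squares. The total is 0.1108, which is 11% lower, or about 6% lower in standard error.

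**6. Does the covariance structure matter?** Take ρ = 0.8, the worst 20% lost, and change unrelated to baseline. Returners' 6-week change is too high by 0.35, and their 3-month change by 0.28. Compound symmetry with common correlation r predicts the 3-month score with slope r/(1 + r), at most 0.5, on the 6-week score. It therefore corrects at most 0.5 × 0.35 = 0.175 and leaves at least 0.28 − 0.175 = 0.105. With baseline SD assumed at 1–4 times the change SD, the residual bias is about 0.10–0.13 SD.

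**The case against.** Several stronger readings are tempting, and the documents do not support them.

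- *Any child who misses a visit is dropped.* No. A child absent at 3 months still counts at 6 weeks, and a missed mid-treatment visit affects neither change.
- *The 3-month result is not comparable.* This is conditional. If all return, the sets are identical. If loss is unrelated to outcome, the mean is unbiased and only less precise.
- *The plan tests the 3-month change by paired t-test.* The sentence says only pre to post. Use at 3 months is an inference: that visit is listed just before the change scores, and no other 3-month method is named. No comparison of 3 months with 6 weeks is planned either. The descriptive means over time need no pairs, but they are not a missing-data method, and robust standard errors change only the stated uncertainty.
- *Unequal loss biases the arm contrast.* The Data analysis section contains no arm contrast. That absence is a separate and larger point.
- *Poor responders will stay away.* This is assumed. If good responders were lost, the bias would reverse. Eligibility requires a caregiver who can bring the child to weekly sessions, and participants are current patients of the centre, both of which may limit loss. Children who leave during treatment may lack both later scores. The sets then do not diverge, and there is no 6-week score to recover.

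It can also be said that in a funding-limited pilot, stating the analysis set and reporting who was missing would expose the problem without a model. That is a fair minimum. It would not correct the estimate, and the model costs little more.

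**Conclusion.** The concern holds in conditional form. The planned method uses only complete pairs and nothing in the plan says what happens otherwise, so the 3-month change falls back on whoever returned. Whether this distorts the result depends on loss that the documents do not quantify.

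Under the assumed 10–30% loss related to poor early response, the spurious gain is about 0.04–0.17 SD of change with moderate selection. The 0.3–0.4 SD figure is an upper bound that needs 30% loss confined to the worst responders. With loss unrelated to outcome there is no bias. The cost is then precision: a likelihood model would lower the variance of an arm's 3-month mean by about 11–13% with 2 of 10 lost and a correlation of 0.8.

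This is a cheap and worthwhile improvement. It does not show that the planned result will be wrong.

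**What to change.** For each outcome, make the main analysis a repeated-measures model fitted by REML, with unstructured covariance over the three visits and Kenward-Roger degrees of freedom. Include all randomised children in their assigned arm, whether or not they complete treatment. Use all observed visits as responses, with a common baseline mean and arm-by-visit terms after baseline. Report the 6-week and 12-week-post-treatment estimates with 95% CIs.

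Keep the paired changes as a sensitivity analysis. Report the number observed and the reasons for missing data by arm and visit. Show the 6-week change both for all children and for those who returned at 3 months, so that a shift in who was measured is visible.

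Name a fallback in advance in case the model does not converge. It should be less restrictive than compound symmetry: for example heterogeneous Toeplitz, or regression of the 3-month score on the baseline and 6-week scores. State that protection under missing-at-random may then be reduced.

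The cost is SAP wording and a little more analysis, with no new data. The downsides are a somewhat more complex model in 20 children (six covariance parameters: three variances and three covariances) and no protection against loss driven by a child's unseen 3-month status.

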- i. Rehabilitation clinic sessions – These will occur up to twice per week for the first 3 weeks and once per week for the second 3 weeks of the 6 week treatment. They are therapist-guided and last up to 90 min consisting of 45 minutes of CCFES-mediated video games and up to 45 minutes of CCFES-mediated functional task practice. Early sessions will focus on training the patient and caregiver to self-administer play of a CCFES-mediated video game at home. As proficiency with one game develops, more games will be introduced. The functional task practice part of the session will engage the participant in using the CCFES system to assist them in practicing using their hand in activities such as lacing beads, throwing balls, eating finger foods, and other play and activities of daily living.
- ii. Home sessions – These consist of CCFES-mediated hand opening and video game exercises with caregiver assistance and supervision as needed. As proficiency develops and more games are added, each home session will increase in duration up to 90 minutes per day, as determined by the treating therapist based on the adherence of each participant. Self report of game difficulty and engagement will be made at the completion of each game (see below)

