## **Outcome Measures**

We will collect the following data during this study.

At eligibility, medical records will be used to provide demographics and baseline information regarding the participant's cerebral palsy, its effects, comorbidities, impairments, and medications taken that might affect the results of this study.

Additionally, we will administer an End of Treatment Questionnaire (15 min) and collect usage and performance logs from the computer and stimulator device in an effort to determine the feasibility of cerebral palsy children using the treatment at home.

At enrollment, we will categorize the participant's general ability to handle objects in daily life using the Manual Ability Classification System (5 min). Using a flowchart, we ask the caregiver to identify which of five levels best describe the child's ability to handle age-appropriate objects. For example, level 1 is "Handles objects easily and successfully", level 2 is "Handles most objects but with somewhat reduced quality and/or speed of achievement", level 3 is "Handles objects with difficulty, needs help to prepare and/or modify activities", level 4 is "Handles a limited selection of easily manage objects in adapted situations, requires continuous support", and level 5 is "Does not handle objects and has severely limited ability to perform even simple actions. Requires total assistance."

At the end of each video game practice session (in lab and at home), we will assess game difficulty and engagement via self-report. A screen will appear at the end of each video game session (180 sessions) that asks the child to rate the difficulty and how engaged they were in the preceding session. The screen will show two visual analog scales (one for difficulty and another for engagement) for the child to report using the computer's touch screen.[6], [7] For difficulty, the choices are: very easy (face with a wide smile), easy (face with a narrow smile), neither easy or hard (neutral face), hard (face with a narrow frown), and very hard (face with a wide frown). For engagement, the choices are: very fun (face with a wide smile), fun (face with a

narrow smile), neither fun or fun or boring (neutral face), boring (face with a narrow frown), and very boring (face with a wide frown). The de-identified data will be saved to the USB drive along with game usage and performance data. This takes 30 seconds during a treatment session.

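### Does the undefined prescribed time make the adherence percentage circular, given a fixed 58-hour dose and therapist-paced home sessions?

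*Combined protocol and SAP*

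**What the plan says.** Under Methods and Procedures the protocol states that "The treatment dose will be the same for both groups". It specifies "10 sessions per wk of self-administered video game training at home" plus two lab sessions a week for three weeks and one a week for the next three, and totals this at 58 hours.

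The two items that follow in the same section describe the sessions in terms of limits. Of the clinic sessions, item i says "These will occur up to twice per week for the first 3 weeks", with a length of up to 90 minutes. Item ii has home sessions "increase in duration up to 90 minutes per day, as determined by the treating therapist based on the adherence of each participant".

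The Data analysis section then derives adherence from stimulator and computer usage data, in order to "calculate the percentage of prescribed treatment time completed by each participant". It does not define the prescribed time. The Outcome Measures section gives the purpose of the logs: they are collected "in an effort to determine the feasibility of cerebral palsy children using the treatment at home".

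**The concern.** One section gives a single total for everyone, while its own sub-items describe a schedule that builds up and is set child by child. The adherence percentage needs a denominator, and both candidates have a drawback.

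- **Therapist-set time.** Past adherence helps decide how much is prescribed. A child who does little may be kept on short sessions and so be judged against a small target.
- **The 58 h total.** The circularity disappears, but a child who follows a gradual build-up exactly scores below 100%.

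This is a pilot, and the logs are meant to show whether home use is feasible. If the same logged hours can read as poor or as complete, the feasibility result could mislead the design of a larger trial, and the stated dose could be taken as what children were actually asked to do.

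**Working it through.** **Reproducing the 58 h.** Session counts and limits come from Methods and Procedures. The number of home days per week is not given, so 5 is an assumption (two sessions a day make ten a week).

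- Clinic: 2 × 3 + 1 × 3 = 9 sessions; 9 × 1.5 h = 13.5 h.
- Home: 5 days × 6 weeks × 1.5 h = 45 h, which is 60 sessions of 45 min.
- Total: 13.5 + 45 = 58.5 h, within 1% of 58 h.
- Working back: (58 − 13.5) h ÷ 60 sessions = 44.5 min per session. On this reading 58 h is close to the maximum and leaves almost no room for a build-up.

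**Other readings of the home limit.**

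- 6 days a week: 13.5 + 36 × 1.5 = 67.5 h.
- 7 days a week: 13.5 + 42 × 1.5 = 76.5 h.
- 90 min for each of 60 sessions: 13.5 + 90 = 103.5 h.

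None of these maxima reproduces 58 h, so the 5-day reading is the likeliest. Under the others, 58 h would leave room for a build-up.

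**Effect of the denominator.** The build-ups below are assumed (5 days a week, all clinic time attended, everything set is done).

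| Home min/day, weeks 1–6 | Home h | Total h | % of 58 h | % of individual prescription | % of 45 h home |
|---|---|---|---|---|---|
| 30, 60, 90, 90, 90, 90 | 450 × 5 ÷ 60 = 37.5 | 51.0 | 88 | 100 | 83 |
| 30, 42, 54, 66, 78, 90 | 360 × 5 ÷ 60 = 30 | 43.5 | 75 | 100 | 67 |

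Both children are fully adherent, so the table shows two different questions being answered. It does not show adherence feeding back into its own denominator.

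**Testing for circularity.** This needs a child who falls short. Suppose 60 min/day is set in week 1 and the child does 40 min/day throughout, so 30 days × 40 min = 20 h is completed.

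- Held at 60 min/day: 30 h set; 20 ÷ 30 = 67%.
- Raised to 90 min/day from week 2: 5 + 25 × 1.5 = 42.5 h set; 20 ÷ 42.5 = 47%.
- Cut to 40 min/day from week 2: 5 + 25 × 40 ÷ 60 = 21.67 h set; 20 ÷ 21.67 = 92%.

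The denominator does respond to adherence, and holding a child back raises the figure. In none of these cases does the child reach 100%, because the early shortfall stays in the cumulative total. The 92% case also goes beyond the text, which says only that "As proficiency develops and more games are added, each home session will increase in duration". Slower escalation fits that wording; a cut for poor adherence is not described.

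**The case for a change.** The best case for acting is that the remedy would be cheap and the ambiguity is real. A fixed total does not fit a duration that rises and is set individually, whatever the day count. The Data analysis section does leave its denominator undefined, and the logs exist to judge home feasibility. In the held-back example the choice of pacing alone moves the figure from 47% to 67%, so a reader shown only one percentage could be misled.

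Those facts stand, but they do not establish a fault in the method. The obvious stronger remedy, one planned home total common to all children as the main denominator, brings back the other drawback: item ii describes no common build-up, so a child who follows a slower individual schedule exactly would again score below 100%. Percent of individual prescription measures whether families did what they were asked. Percent of a nominal total measures how much of the intended exposure was delivered. Both are legitimate, and preferring one is a trade-off. What remains is labelling: saying which denominator was used and giving completed hours beside it. An analyst would normally do this, and completed time is already logged. The individual percentage also requires each child's set time to be on record, but nobody could calculate it without that.

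**Conclusion.** No change to the plan follows. The undefined term is a gap that analysts fill sensibly. Read naturally, time prescribed to each participant is what the therapist set, and reporting hours alongside the percentage makes either choice interpretable.

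The consequence is limited. Adherence is an additional descriptive measure in a pilot of 20 whose stated aim is to estimate efficacy. No threshold, hypothesis test or progression rule depends on it. The four change-score outcomes do not use it, and nothing here points to a difference between arms. Any circularity is partial, since clinic frequency is not tied to adherence, and it is conditional on the therapist-set reading.

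The fixed 58 h and the individually paced limits do sit awkwardly together within Methods and Procedures. The sponsor must reconcile that wording, and I take no view on which hours or pacing should apply. That 58 h is about the maximum rests on the assumed 5 home days a week. The percentages for build-ups and shortfalls rest on assumed schedules, because the documents give no starting duration or pace.
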